To achieve our long term goal of integrating lifestyle modifications to reduce cancer risk and related disparities for rural populations, understanding the underlying biological mechanism of weight loss, body composition, and inflammation is critical. However, empirical evidence documenting the efficacy of lifestyle weight loss interventions in rural populations is limited. Among completed or recently awarded trials (as of January 2020), none measured body composition and inflammation markers. Estimating the effect of lifestyle interventions on weight loss, body composition, and disease risk factors (inflammatory markers, lipid profiles) in rural populations is essential for the design and implementation of evidence-based approaches on a larger scale.

This study will recruit up to 50 obese rural Ohio residents and randomly assigned to a 15-week telephone-based weight loss (n=30) or an active control group (up to 20). The study objective is to determine the feasibility and preliminary efficacy of a 15-week telephone-based weight loss intervention on weight, body composition, and inflammatory markers, with tailored strategies and group messages to address barriers, self-efficacy, and social support for rural Ohio populations. We will utilize a novel and applicable point-of-care approach to assess body

composition, lipid profiles, and cancer risk factors in rural community settings. The Specific Aims for this study are:

1. To determine the feasibility and acceptability of a 15-week telephone-based weight loss intervention among obese rural residents.

We hypothesize that 80% of obese rural residents who participate in the study will complete the assigned intervention (**feasibility**), and 80% of the participants in the intervention group will engage in at least 75% of the weekly telephone counseling session (**acceptability**). During the 15-week weight loss intervention, we anticipate the minimal occurrence of intervention-related adverse events.

2. To estimate the preliminary efficacy of the lifestyle modifications on weight loss, body composition (fat mass, fat percentage), inflammatory biomarkers (IL-6, TNF- α , and CRP), and other disease risk factors (lipid profiles).

We hypothesize that the lifestyle intervention will result in substantial improvements in weight loss, fat mass, fat percentage, IL-6, TNF- α , CRP, and lipid profiles (with moderate effect size), compared to the active control group.

B BACKGROUND AND RATIONALE

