We considered using a standard measure of body composition using Dual-energy X-ray absorptiometry (DXA) but opted not to as this is likely to add the burden of travel to facilities equipped with DXA. However, we will assess body composition using a 3-D Styku body scanner, which is portable to rural community-settings and can provide valid and reliable data on body composition. Together with using Cholestech LDX to evaluate participants' lipid profiles, the proposed study is innovative to test new point-of-care approaches to assess disease risk factors in rural populations.

D DATA HANDLING AND ANALYSES

D.1. Outcome Analysis Plan

D.1.a Primary outcome

The feasibility of completing the study is defined as the percentage of enrolled participants who complete the study. If we observe an 80% completion rate in the weight loss intervention group (n=30), the 85%, 90%, and 95% confidence intervals (CIs) for the completion rate would be (69.5, 90.5), (68.0, 92.0), and (65.7, 94.3), respectively. If the true completion rate is 80%, we have 95% power to rule out the unacceptable 50% completion rate with 95% confidence (one-sided).

The acceptability of the weight loss intervention is the percentage of participants in the weight loss intervention group who engage at least 75% of the weekly telephone counseling session. Intervention-related adverse events, satisfactory, and other feasibility assessments, such as the percent of initial contact to enrollment, reasons for consent refusal, barriers to adherence to weekly goals, and reasons for drop-out will also be assessed.

D.1.b Secondary outcome

Significance test for the preliminary efficacy of the lifestyle intervention will quantify the difference in means using repeated measures analysis of variance (ANCOVA) statistical model to adjust baseline values and control for the effect of age. The sample size of 30 participants in the weight loss group and at least 15 in the active control group is feasible to recruit for a pilot/preliminary efficacy study that accounts for a projected attrition rate of 20% yet also still provides adequate power to detect meaningful, moderate to large effect size (0.54-0.72) on weight loss, body composition, inflammatory markers, and lipid profiles.

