also a risk of muscle injury, which may require medical attention, may take several months to heal, and may limit activities of daily living for a period of days, weeks, or months. Participants will be informed that there is an increased risk with starting a physical activity program and be advised of all of the potential risks. Additionally, [name] and research staff with training in exercise physiology and behavioral changes will be directly involved in conducting physical fitness tests and delivering exercise components.

There is a slight risk of breach of confidentiality, but steps are in place to protect participants' personal information. Electronic data will be stored behind a firewall and accessed only by study staff through password-protected computers. Paper-based data will be stored in a locked cabinet within a locked file room.

Collectively, the participants will be assuming no more than minimal risk in completing the assessment protocol and the minimal risk inherent to completing the assessments will be mitigated via stringent pre-test medical screening and during testing supervision.

E.2 Benefits of participation

Participants may gain awareness of healthy eating and physical activity from evidence-based program. Participants in the telephone-based counseling group will receive a physical activity tracker (e.g., Fitbit) at the beginning of the study, and weekly telephone-based weight loss counselling for 15 weeks. Participants in the active control group will also receive a physical activity tracker and lifestyle modification manual at the end of the study. All participants will receive regular body weight, body composition, and blood tests for lipid profiles and inflammatory biomarkers free of charge.

E.3 Adverse events

Adverse events, including any unfavorable and unintended sign (e.g., abnormal laboratory finding or symptom) will be collected as they occur, regardless of whether it is considered related to the weight loss intervention. Musculoskeletal injuries and previously undocumented major medical events incurred during the intervention will be systematically collected on all participants during the study period using standardized forms from our prior work. Patients will have instructions to contact the PI or their primary health providers to discuss and manage any possible side effects. The PI, study coordinator should immediately be contacted in the event such a problem arises.

E.3.a Severity

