- 1) Serious adverse event: Any adverse event that is fatal or life threatening, is permanently disabling, requires inpatient hospitalization or prolongs hospitalization, or results in a congenital anomaly or birth defect;
- 2) Life-threatening event: Any adverse event in which the subject is at immediate risk of death from the reaction as it occurs; does not include a reaction that, if it occurs in a more serious form, might cause death;
- 3) Unexpected event: Any adverse event that is not identified in nature, severity, or frequency in the investigator brochure, study protocol, consent form, or IND application; or the event is more serious than anticipated.

E.3.b Association

- 1) Definitely Related: An adverse event that has a timely relationship to the administration of the study intervention and follows a known pattern of response for which no alternative cause is present;
- 2) Probably Related: An adverse event that has a timely relationship to the administration of the study intervention and follows a known pattern of response, but for which a potential alternative cause may be present;
- 3) Possibly Related: An adverse event that has a timely relationship to the administration of the study intervention, follows no known pattern of response, but a potential alternative cause does not exist;
- 4) Unrelated: An adverse event for which there is evidence that it is definitely related to a cause other than the study intervention; in general, no timely relationship to the administration of the drug/procedure exists, or if so, the event does not follow a pattern of response and an alternative cause is present.

E.3.c Documentation

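### E.3.b leaves a timely adverse event with no known pattern and only a potential alternative cause outside every related category, so the intervention-related count may be too low

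*Combined protocol and SAP*

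**What the plan says.** E.3.b (Association) grades adverse events in four categories. The first three all require a timely relationship to the intervention and differ as follows:

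- Definitely Related: the event "follows a known pattern of response for which no alternative cause is present".
- Probably Related: the event "follows a known pattern of response, but for which a potential alternative cause may be present".
- Possibly Related: the event "follows no known pattern of response, but a potential alternative cause does not exist".

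Item 4, Unrelated, has two parts. It opens with events for which "there is evidence that it is definitely related to a cause other than the study intervention". It then adds, as a general remark, that the timing does not fit or, if it does, "the event does not follow a pattern of response and an alternative cause is present".

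E.3.c (Documentation) has staff record a suspected cause. It uses the grades possibly and probably for a list that sets study treatment beside disease progression, other medication, other illness and further factors.

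Relatedness is used in three places. Aim 1 says "we anticipate the minimal occurrence of intervention-related adverse events". D.1.a lists "Intervention-related adverse events, satisfactory, and other feasibility assessments" among the items to be assessed in addition to completion and session engagement. E.3.d sends related events that involve risk, but do not need prompt reporting, to the IRB in summary at continuing review.

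Two provisions do not depend on relatedness. E.3 collects adverse events "regardless of whether it is considered related to the weight loss intervention", and the 10-day rule for serious adverse events in E.3.d carries no such condition.

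**The concern.** A causality scale should be ordered, so that weaker evidence leads to a weaker grade, and exhaustive, so that every event has one place. On the alternative-cause criterion this scale is not ordered: Probably Related tolerates a competing explanation, and Possibly Related, the weaker grade, does not. The event that most readers would call possibly related has plausible timing, an unfamiliar presentation, and another explanation that is conceivable but not shown. That event is barred from the category.

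Item 4 does not settle where it goes instead. Its opening condition asks for positive evidence of another cause, while its closing clause seems to need only that one exists. Neither part says what to do when the alternative is merely potential. Two raters could handle the same event differently, and neither would be following item 4 in full.

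At stake are the number of intervention-related adverse events reported with the feasibility results and the content of the related-event summary to the IRB. Any effect of the restriction runs toward the minimal occurrence that Aim 1 expects.

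**Working it through.** The plan attaches no figure to this point, so the check is a reading of the definitions against each other.

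**Step 1. Timely events, by known pattern and alternative cause.** The inputs are items 1 to 4 of E.3.b.

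| Known pattern | Alternative cause | Related category that fits | Does Unrelated fit? |
|---|---|---|---|
| yes | none | Definitely | no |
| yes | potential | Probably | no |
| no | none | Possibly | no |
| no | potential, unproven | none | opening condition not met; closing clause arguably met |

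Three of the four timely combinations have a related category and one has none.

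**Step 2. The fourth row under item 4.**

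- Strict reading: the opening condition governs. An unproven alternative is not evidence of a definite other cause, so the event is not Unrelated either and has no category.
- Lenient reading: the closing clause suffices, and a potential cause counts as one that is present. The event is Unrelated, although nothing shows that the intervention was not the cause.

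The event is outside the related categories on both readings.

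**Step 3. E.3.b against E.3.c.** E.3.c lets staff name study treatment as a possible cause on a form that lists competing causes beside it. E.3.b withdraws the Possibly grade as soon as a competing cause is conceivable. A rater who works from the E.3.c form could therefore record as possible an event that E.3.b excludes.

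**Step 4. Direction and size.** Let R be the number of events in the first three rows and u the number in the fourth.

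- Count if E.3.b is followed: R.
- Count if some raters follow the sense of E.3.c: between R and R + u.
- Count if a potential alternative cause no longer excludes an event: R + u.

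Since u cannot be negative, the restriction can lower the related count but never raise it. The documents give no adverse event rates, so u cannot be computed.

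**Step 5. Can the fourth row occur here?** C.3.b lets people with conditions such as heart problems, insulin-dependent diabetes or poorly controlled blood pressure enrol with medical clearance. C.3.e has weight loss participants report existing conditions, injuries and recent surgery at baseline. Potential alternative causes will therefore sometimes be on file. E.1 names muscle soreness, muscle injury and venipuncture effects as the physical risks, so an event of another kind may have no documented pattern.

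**The case against.** The strongest reply is that item 4, read to its end, covers the fourth row: it describes a timely event without a pattern for which there is an alternative cause. The four combinations then map to Definitely, Probably, Possibly and Unrelated, and the scale is complete. On this view the scale works on two features. Pattern separates the first two grades from the third, and alternative cause separates events within each pattern group. Placing the fourth row in Unrelated is then a design choice rather than an error.

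Much of this stands. A reader might infer that the fourth row has no category at all; that holds only on the strict reading of item 4. A reader might also infer that related events are under-counted as a matter of fact. The documents do not support that: they give no event rates, and there is an under-count only against a meaning of possibly related that is broader than the one E.3.b states.

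The reply does not remove the conflict within item 4. The closing clause is a general remark attached to a condition that asks for definite evidence, and a merely potential alternative does not meet that condition. Nor does the reply explain why E.3.c grades study treatment as a possible cause alongside competing ones.

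The reply is also right that the consequences are limited. The harms named in E.1 would match a known pattern and be rated Definitely or Probably Related, so the disputed row is probably small. E.3.c keeps the suspected cause on record, which allows re-rating. It would be too strong to infer that the feasibility conclusion is biased: feasibility is defined by completion and acceptability by session engagement, and related adverse events are assessed alongside them without a threshold or test.

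**Conclusion.** The point holds as a minor defect of definition. One of the four timely combinations, no known pattern with a merely potential alternative cause, falls outside every related category. It is then recorded as Unrelated without the definite evidence that item 4 opens by requiring, or it is classified inconsistently. The intervention-related count in Aim 1 and D.1.a and the IRB summary of related events may be too low. The possible error runs in one direction and its size cannot be derived.

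This rests on two assumptions: that at least some events of this kind occur, and that an event with plausible timing and no established other cause should not lose related status merely because another cause is conceivable.

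A reader might go further and infer that safety surveillance is weakened. The documents do not support that. Events are collected whatever their attribution, serious events go to the IRB within 10 days without a relatedness condition, and no decision rule uses the related count.

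**What to change.** Three short edits:

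1. In E.3.b, reconcile items 3 and 4 so that the grades are ordered and exhaustive. A merely potential alternative cause should not by itself remove a timely event from the related categories. One way is to let Possibly Related admit a potential alternative cause and to make the closing clause of Unrelated agree with its opening condition.
2. Align the suspected-cause wording in E.3.c, and the adverse event form, with the revised grades.
3. State in D.1.a which grades count as intervention-related, for example Definitely, Probably and Possibly together.

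The cost is a few lines in the protocol and the form, with no change to procedures, sample size or analysis method. The reported related-event count may rise slightly; reporting it by grade would let readers see where any rise comes from.
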